## **9 STATISTICAL CONSIDERATIONS**

### **9.1 General Design Issues**

The over-riding objective of this proposal is to conduct a pragmatic cluster-randomized controlled trial (RCT) of “Aligning Patient Preferences – a Role Offering Alzheimer’s patients, Caregivers, and Healthcare providers Education and Support (APPROACHES)” that aims to improve ACP and goal-directed outcomes in nursing home patients with ADRD. In the R33 phase, we will conduct the full pragmatic RCT in partnership with 2 nursing home corporations (Signature HealthCARE and Miller’s Health Systems) who operate a combined total of 142 diverse facilities in 8 states. Consistent with the spirit of a pragmatic trial, we will use existing data sources including electronic health records (EHR), the Minimum Data Set 3.0 (MDS), and Medicare Claims data to characterize the cohort and measure outcomes. Hospital transfers over 12 months among ADRD patients is the 1o trial outcome.

### **9.2 Sample Size and Randomization**

#### **Power Calculations.**

The implementational advantages of cluster RCT are gained at the expense of reduced analytical power, as compared to a simple RCT. Reduction of power is proportional to the intracluster correlation (ICC) coefficient  $\rho$ , which represents the strength of correlation among subjects within the same cluster. The within-cluster correlation has a correlate – the between cluster variation, which is commonly expressed as the coefficient of variation (CV). Larger ICC or CV values will lead to bigger variance inflation and more power loss.

A power analysis was conducted using preliminary data from the Minimum Data Set (MDS) provided by CMS. We estimated that the between-cluster CV would be less than 0.5. Assuming that the two treatment arms have similar CV values of a similar magnitude, we calculated the power for detecting 20% reduction in rate of hospital admission by the proposed intervention. Our analysis showed that with 120 facilities (60 per arm) and an average of 50 residents per facility, we will have 81% power to detect a 20% difference in the rate of hospitalization (1.0 per resident year in the control group vs 0.8 per resident year in the intervention group), by using a Poisson regression analysis

with 0.05 level of significance. We note that the power estimate is likely to be conservative because in the actual analysis, we plan to control for the effects of the covariates; the reduced variability explained by the covariates will increase the power.

### **9.3 Interim analyses and Stopping Rules**

We will not be conducting an interim analysis or developing rules for stopping the trial early for several reasons. The planned intervention of a trained ACP Specialist who will augment usual care is unlikely to cause harm. The IRB has determined that this study is minimal risk. Particularly given the delay in obtaining Medicare claims for determining the primary outcome, hospitalization or emergency department visits, it will not be feasible to determine the differences in this outcome between the intervention and control groups until the end of the 12 month outcome observation period.

### **9.4 Outcomes**

#### **9.4.1 Primary outcome**

9.4.1.1 Hospital transfers over 12 months among ADRD patients

#### **9.4.2 Secondary outcomes**

9.4.2.1 Hospice enrollment over 12 months among ADRD patients

9.4.2.2 Death in hospital over 12 months among ADRD patients

### **9.5 Data Analyses**

Design consideration. The R33 phase of the study has two aims: (Aim 1 – Primary) To compare hospital transfers (admissions and emergency department visits) over 12 months between ADRD patients in the intervention and control facilities; and (Aim 2 - Secondary) assess the interventional effect of the ACP Specialist Program on hospice enrollment and place of death. Towards these ends, we employ a cluster RCT design. With this design, randomization will be carried out at the nursing home level, stratified by nursing home corporate ownership and baseline hospitalization transfer rates (low versus high). All patients at a given nursing home will have the same intervention assignment. The trial outcomes will be analyzed at the individual patient level and reported at the facility level. The cluster RCT with nursing home randomization is chosen because of its ability to simultaneously maximize the implementational feasibility and minimize the contamination risk. Counts of hospital transfers and emergency department visits incurred by individual ADRD patients during the follow-up period will be considered as the primary outcome. We designed the trial to ensure adequate power for the hypothesis concerning the primary outcome. Average age and proportion of female patients is similar across our nursing home partner facilities and the U.S. The % of Black patients ranges from 6-17% across the population of our partner nursing homes. About half of nursing home patients have a dementia diagnosis. This is similar for our partner facilities.

Analysis will be carried out in an intention-to-treat (ITT) framework, which gives a pragmatic estimate of the interventional benefit. The ITT analysis will use data from all eligible patients in randomized facilities, regardless of the level of facilities' adherence to the study protocol and patient attrition. ITT is a preferred approach for pragmatic trials

because the analysis generates estimates of treatment effectiveness in a more realistic way. In fact, clinical effectiveness can be severely overestimated if ITT analysis is not performed. Within the ITT framework, we propose to analyze the trial data using appropriate generalized linear models. Specifically, we plan to compare the rates of hospital admissions in patients residing in the intervention vs control facilities. In line with intention-to-treat principles and our cluster randomized design, hospitalizations will be analyzed at the facility level, including for residents who moved across intervention and control buildings during the study period. Group assignment will be based on the facility each resident was first admitted to during the intervention period. Thus, some residents may have a documented ACP encounter in intervention facilities but also spent some time in control facilities. The analysis will be carried out using an appropriate count data regression model, length of observation will be adjusted as an offset parameter. We will test the levels of extra-Poisson variation to determine if a Poisson regression model is sufficient for the analysis. If the level of variation is beyond what can be accommodated by the Poisson model, we will consider using negative binomial regression. Similarly, we will test the presence of extra zeros that beyond the Poisson or negative binomial models. If necessary we will consider the use of zero-inflated Poisson or negative binomial regression analysis. Correlations among outcomes measured from residents in the same facility will be accounted for by adding random facility effects into the regression models. This analytical approach handles missing data (early dropout due to death or transfer to hospice) more easily because of the inclusion of offsetting parameters in the model.

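### Section 9.5 allows a data-driven switch of the primary analysis to a zero-inflated model, whose treatment coefficient is in general not the overall rate ratio that Aim 1 and the power calculation concern

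*Combined protocol and SAP*

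**What the plan says.** Aim 1 (section 1.1) compares hospital transfers, defined as admissions plus emergency department visits, and H1 expects fewer in the intervention homes. Section 9.5 defines the primary outcome as "Counts of hospital transfers and emergency department visits incurred by individual ADRD patients" and describes the comparison this way: "we plan to compare the rates of hospital admissions in patients residing in the intervention vs control facilities". It adds that "length of observation will be adjusted as an offset parameter" and that facilities enter as random effects. The power calculation in section 9.2 is for a single rate per arm, "1.0 per resident year in the control group vs 0.8 per resident year in the intervention group".

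The model is chosen from the data in two steps. A test of extra-Poisson variation may lead from Poisson to negative binomial regression. Then "we will test the presence of extra zeros that beyond the Poisson or negative binomial models", followed by "If necessary we will consider the use of zero-inflated Poisson or negative binomial regression analysis". The section does not say whether arm would enter the zero part, the count part or both. It also does not say which coefficient or derived quantity would then decide Aim 1.

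**The concern.** Under Poisson or negative binomial regression with an offset there is one treatment coefficient, and it is a rate ratio. A zero-inflated model splits residents into a share who can never have an event (structural zeros) and the rest, who have events at some rate. The count-part coefficient is the rate ratio among the rest only. If arm is also in the zero part, there is a second coefficient, the odds ratio of being a structural zero.

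If the structural-zero share differs between arms, neither coefficient equals the overall rate ratio. Such a difference is plausible here. Section 2.2 links documented preferences for less aggressive treatment to lower hospitalization, and a resident with such a preference might never be transferred. A real reduction in transfers could then appear mainly in the zero part, while the count part shows little. Because the switch follows a test on outcome data, the decision on what counts as the primary result would also be taken after the data are seen.

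**Working it through.** **What the plan is powered for.** Inputs from section 9.2: 60 facilities per arm, 50 residents each, rates 1.0 and 0.8, two-sided 0.05 (sidedness assumed). The between-facility CV, k, is given only as below 0.5. The Hayes-Bennett formula is

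z = sqrt{ (60 − 1)(1.0 − 0.8)² / [ (1.0 + 0.8)/50 + k²(1.0² + 0.8²) ] }, power = Φ(z − 1.96).

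- k = 0.40: z = sqrt(2.36/0.2984) = 2.81, power 80.3%.
- k = 0.50: z = sqrt(2.36/0.446) = 2.30, power 63.3%.

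The stated 81% is consistent with k of about 0.40, but the value used is not stated. What matters for this point is that the powered quantity is the overall ratio, 0.80.

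**Arm in both parts.** Let p be the structural-zero share and m the rate among the rest. The overall rate is (1 − p)m, so

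count-part ratio m₁/m₀ = overall ratio × (1 − p₀)/(1 − p₁).

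At a true overall ratio of 0.80 and p₀ = 0.30 (assumed):

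| p₁ | Count-part ratio |
|---|---|
| 0.30 | 0.80 × 0.70/0.70 = 0.80 |
| 0.37 | 0.80 × 0.70/0.63 = 0.89 |
| 0.44 | 0.80 × 0.70/0.56 = 1.00 |

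The last row is the extreme case, with the whole effect in the zeros; the zero-part odds ratio is (0.44/0.56)/(0.30/0.70) = 1.83. The choice of 0.30 is not critical. For p₀ from 0.10 to 0.40, placing the whole effect in the zeros always gives a count-part ratio of 1.00, with zero-part odds ratios from 3.50 down to 1.63.

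**Arm in the count part only.** Here a common zero share is forced on both arms. The large-sample limit of a zero-inflated Poisson fit (maximum of the expected log-likelihood, no facility effects) was found numerically for two assumed observation patterns: 30%, 20% and 50% of residents observed for 0.25, 0.5 and 1 year, or all for one year.

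| Zero shares | Mixed observation | One year |
|---|---|---|
| 0.30 vs 0.30 | 0.80 | 0.80 |
| 0.30 vs 0.37 | 0.82 | 0.83 |
| 0.30 vs 0.44 | 0.85 | 0.87 |

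The departure from 0.80 is much smaller but does not vanish.

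**If the overall ratio is derived from a zero-inflated fit.** Section 9.2 says "in the actual analysis, we plan to control for the effects of the covariates". With covariates in the zero part, no single formula in p and m is enough. At a common zero-part odds ratio of 1.83 and no count effect, control shares of 0.1, 0.3 and 0.5 give ratios of 0.92, 0.80 and 0.71. Averaged over equal thirds the ratio is (0.831 + 0.560 + 0.353)/(0.9 + 0.7 + 0.5) = 0.83.

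Observation time matters as well. Section 9.5 describes "missing data (early dropout due to death or transfer to hospice" as handled by the offset, and Aim 2 expects more hospice enrollment with the intervention, so observation time may differ by arm. As an example, take residents with rate 0.8 over 1 year or rate 3 over 0.25 year, with no effect on either rate, and short-observation shares of 30% vs 40%:

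- control: (0.7 × 0.8 + 0.3 × 0.75)/(0.7 + 0.3 × 0.25) = 0.785/0.775 = 1.013;
- intervention: (0.6 × 0.8 + 0.4 × 0.75)/(0.6 + 0.4 × 0.25) = 0.780/0.700 = 1.114.

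The person-time ratio is 1.10, while a ratio standardised within the two groups is 1.00. Both can be called an overall rate ratio.

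**The case against.** The strongest reply is that the plan's intent is clear: it compares rates, with an offset, and powers on a rate, so a sensible analyst would report an overall ratio whatever the model. That supports the fix as matching the sponsor's intent. It does not close the gap, because the count part of a zero-inflated model also yields a rate ratio, only for a different group of residents. The sentence on comparing rates also names no effect measure.

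Second, the plan never says that arm would be in both parts. With arm in the count part only there is one coefficient, and it lies much nearer the overall ratio. This stands, and the 1.00 in the illustration should be read with that condition.

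Third, the switch is only to be considered if needed. In simulations with ordinary gamma heterogeneity and no structural zeros, zero-inflated Poisson beat negative binomial on AIC in 0% of data sets, and zero-inflated negative binomial did so in 7 to 8%. This too stands: the plan's own sequence of tests was not simulated, and how often a switch would occur is unknown.

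A reader might infer that a switch would produce false claims of benefit. The algebra allows it: with equal overall rates and zero shares of 0.30 vs 0.125, the count-part ratio is 0.70/0.875 = 0.80. But this needs the intervention to make more residents prone to transfer while cutting the rate among them by exactly the offsetting amount. Nothing in the documents suggests that, and with arm in the count part only the limit is 0.95 to 0.96.

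**Conclusion.** The gap is real but conditional. If the zero-inflated option is used and structural-zero shares differ by arm, the treatment coefficient does not estimate the ratio that H1 and the power calculation concern. At a true 0.80 with assumed shares of 0.30 vs 0.44, it is 1.00 (arm in both parts) or about 0.85 to 0.87 (arm in the count part only). With equal shares there is no problem. These figures rest on assumed zero shares and observation patterns and say nothing about how likely the switch is.

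A reader might conclude that the plan contradicts itself or makes the count part the primary test. It does neither; it leaves the choice open. Nor does this point show that the Poisson or negative binomial analysis is unsound, since each already has one treatment rate ratio. The unstated CV behind the 81% is a separate matter.

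The wording also needs reconciling: sections 9.2 and 9.5 speak of admissions where Aim 1 and section 9.4.1 speak of transfers, which include emergency department visits. The point is worth correcting before outcomes are analysed by arm.

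**What to change.** In section 9.5, state that Aim 1 is tested by the single treatment rate ratio for all transfers (admissions plus emergency department visits) from the Poisson or negative binomial model with the offset and random facility effects already planned. State that zero-inflated fits are sensitivity analyses only. Bring the admissions wording in sections 9.2 and 9.5 into line with Aim 1.

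If a zero-inflated model is kept as a primary option, require that the test be the overall rate ratio derived from both parts, with an interval that respects facility clustering. One way is to predict each resident's expected transfers under each arm, sum over residents, take the ratio, and use a facility-level bootstrap or the delta method; the bootstrap was not tried here. The text must also name one estimand, including how observation time is treated, because it ends at death or hospice transfer and may differ by arm.

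The cost is a few sentences, plus some programming if the zero-inflated option stays primary. The downside is a model slightly less tailored to the observed distribution and a small possible loss of power. In simulations with truly zero-inflated data (120 facilities of 50 residents, assumed CV 0.40, mixed observation times), the loss relative to the ratio derived from the zero-inflated fit was under 1 percentage point for negative binomial and about 2 to 3 for Poisson with facility-robust standard errors. Other observation patterns were not run.

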### **3 STUDY DESIGN**

A total of 142 nursing homes will be randomized to either an intervention or control arm within each corporation (Signature, N= 109; Miller’s, N= 33). In intervention nursing homes, a nursing home provider (e.g. social worker) will be trained as an ACP Specialist who will work with nursing home leaders to: i. Consolidate nursing home ACP procedures; ii. Train and educate staff; and iii. Facilitate ACP with patients and their family caregivers. Control nursing homes will apply the usual ACP practices. The implementation period is expected to be 18 months. All ADRD patients in the nursing homes during the implementation will be followed for 12 months.

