### **4 SELECTION AND ENROLLMENT OF PARTICIPANTS**

Facilities will be randomized to either the control arm or the intervention arm. This selection will take into account the choice of each organization considering half the organizations facilities are included in each arm.

The focus of the ACP Specialist will be patients with ADRD who reside in the nursing homes during the initiative, though other patients residing in the nursing home may benefit from it in keeping with the spirit of a pragmatic trial. Only patients with ADRD will be included in the analysis. ADRD is defined to include cognitive impairment or a documented diagnosis of dementia in the MDS. Patients will be excluded if they are currently enrolled in hospice at the start of the intervention period.

Eligible facilities who agree to participate in the trial will be stratified at two levels: corporate ownership (Signature HealthCARE and Miller's Health Systems) & average number of hospital transfers per 1000 person-days alive using 2017 MDS data provided by CMS. Facilities will be grouped into low versus high hospitalization rates, using the median rate for the nursing home system as the threshold value for dichotomization. Facilities will be randomized to the intervention or control within each strata at a 1-to-1 ratio. Specifically, randomization will occur at the facility level, meaning that all patients with ADRD in the intervention buildings are eligible for inclusion in the trial. Following random assignment, we will use all available facility and patient-level data to test the balance of the intervention and control arms.

Nursing home characteristics will be obtained from nursing home corporate partners and the MDS. Potentially eligible nursing homes will be reviewed by the Data Management and Analysis Workgroup in preparation for potential inclusion in the pragmatic cluster RCT. Problematic or unstable facilities will be removed in consultation with nursing home corporate leaders prior to randomization.

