## **6 STUDY PROCEDURES**

### **6.1 Description of Evaluations**

#### 6.1.1. Enrollment, Baseline, and/or Randomization

Nursing home Eligibility: All Medicare-certified nursing homes are eligible at Signature HealthCARE and Miller's Health Systems.

Nursing home Recruitment & Characteristics:

The ACP Specialist Program will be rolled out as a corporate initiative and nursing home Executive Directors will be requested to participate in the initiative by nursing home corporate leadership. It is anticipated all nursing home Executive Directors who are approached will agree to participate.

Nursing home corporate partners each provided data about key nursing home characteristics. At the time of randomization Signature HealthCARE owns 109 nursing homes in 8 states, with a total of 8,811 beds; 43% are rural. Miller's Health Systems owns 33 nursing homes, all in Indiana with 3,066 beds; 55% are rural. The mix of rural and urban facilities will provide a rich environment for this pragmatic trial. Self-reported 30-day hospital readmission rates for 2016 range from 13% for Miller's Health Systems and 17% for Signature HealthCARE nursing homes.

Random Assignment: Nursing homes will be sorted into groups that are comparable on hospital transfer rates. Eligible facilities who agree to participate in the trial will be stratified at two levels: corporate ownership (Signature HealthCARE and Miller's Health Systems) & average number of hospital transfers per 1000 person-days alive using 2017 MDS data. Facilities will be grouped into low versus high hospitalization rates, using the median rate for the nursing home system as the threshold value for dichotomization. Facilities will be randomized to the intervention or control within each strata at a 1-to-1 ratio. Specifically, randomization will occur at the facility level, meaning that all patients not currently on hospice at the start of the intervention period in the intervention buildings are eligible for inclusion in the trial. The intervention focuses on patients with ADRD, but other residents of intervention facilities are not excluded. Following random assignment, we will use all available facility and patient-level data to test the balance of the intervention and control arms.

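### The covariates promised in Section 9.2 are never named, so neither stratification factor is secured in the primary model, and power is lost if the strata predict transfers

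*Combined protocol and SAP*

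**What the plan says.** **Allocation.** Section 3: "A total of 142 nursing homes will be randomized to either an intervention or control arm within each corporation". Sections 4 and 6.1.1 add the second factor, "average number of hospital transfers per 1000 person-days alive using 2017 MDS data provided by CMS", cut at each system's own median, with 1:1 allocation inside each stratum. Section 9.5 repeats, as a design feature, that randomisation is "stratified by nursing home corporate ownership and baseline hospitalization transfer rates (low versus high").

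**Primary model.** Section 9.5 specifies a count regression (Poisson, with negative binomial or zero-inflated forms if needed) comparing the arms, with length of observation as an offset. Clustering is handled in one sentence: "Correlations among outcomes measured from residents in the same facility will be accounted for by adding random facility effects into the regression models". No fixed effect other than arm is listed.

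**Covariates.** Section 9.2 says that "in the actual analysis, we plan to control for the effects of the covariates" and gives this as the reason for calling the power estimate conservative. No section names a covariate. Sections 4 and 6.1.1 plan tests of balance between arms, but do not say what follows from them for the model.

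**The concern.** Stratified allocation makes the arms nearly equal on whatever the strata explain, so that part of the between-facility variance drops out of the treatment contrast. A model without stratum terms does not know this. It leaves the between-stratum variance in the random facility effect and charges it to the standard error. Intervals are then too wide, the test tends to reject less often than 5% under the null, and power is lost.

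This matters only if the strata predict transfers. One stratifier is the facility's own earlier rate of the primary outcome, so some prediction is plausible. Section 6.1.1 also suggests that the corporations differ: self-reported 2016 30-day readmission was 13% in one and 17% in the other.

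There is a second cost. An unlisted covariate set leaves the adjustment of the primary test open until the data are in hand.

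**Working it through.** **Inputs from Section 9.2:** rates λ0 = 1.0 and λ1 = 0.8 per resident-year; 60 facilities per arm; m = 50 residents per facility; significance level 0.05 (taken as two-sided, since sidedness is not stated); between-facility CV k below 0.5 (the value used is not given). **From Section 3:** 142 facilities (109 + 33), or 71 per arm.

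**Assumed, because the documents do not give it:** r, the correlation between a facility's 2017 rate and its trial-period rate, over the range 0 to 0.7.

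**Step 1. The plan's figure.** With c facilities per arm (Hayes–Bennett form),

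D = (λ0 + λ1)/m + k²(λ0² + λ1²), power = Φ(√c·(λ0 − λ1)/√D − 1.96).

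- k = 0.4, c = 60: D = 0.036 + 0.16 × 1.64 = 0.2984. Power = Φ(√(60 × 0.04/0.2984) − 1.96) = Φ(0.876) = 80.9%, which is the plan's 81%.
- k = 0.5, c = 60: D = 0.036 + 0.25 × 1.64 = 0.446, and power is 64.0%.

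A CV near 0.4 is therefore consistent with the stated power. The results below use 0.4 and the plan's upper bound of 0.5. The 81% includes no credit for strata or covariates.

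**Step 2. The mechanism in closed form (71 per arm).** A median split of a normal log rate captures about 0.64 r² of the between-facility variance (2/π = 0.637), ignoring any difference between corporations. Without strata the model charges D. The variance actually left under stratified allocation is D_s = 0.036 + (1 − 0.637r²)·1.64k². With a continuous baseline it is D_c = 0.036 + (1 − r²)·1.64k².

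Example with k = 0.5 and r = 0.5, where √71 × 0.2 = 1.685:

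- D = 0.446, D_s = 0.036 + 0.841 × 0.41 = 0.381, D_c = 0.036 + 0.75 × 0.41 = 0.3435.
- Unadjusted: Φ((1.685 − 1.96 × 0.668)/0.617) = Φ(0.610) = 72.9%.
- Strata: Φ(1.685/0.617 − 1.96) = Φ(0.771) = 78.0%.
- Continuous baseline: Φ(1.685/0.586 − 1.96) = Φ(0.915) = 82.0%.
- Unadjusted type I error (both rates 1.0): the charged variance is 0.04 + 0.5 = 0.54 and the actual variance 0.04 + 0.841 × 0.5 = 0.4605. The ratio of standard errors is 1.083, so the error is 2(1 − Φ(1.96 × 1.083)) = 3.4%.

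Over the range of r, the unadjusted type I error from this formula is 5.0% (r = 0), 4.4% (0.3), 3.4% (0.5) and 2.0–2.1% (0.7).

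**Step 3. Simulation of the count model.** 109 + 33 facilities, corporation-specific median split, 1:1 within four strata, 50 resident-years per facility, log-normal facility rates, and Poisson regression with a normal random facility effect and a Wald test. There were 10,000 trials per cell (Monte Carlo standard error 0.1–0.4 points for power, about 0.2 for type I error). Power (%) for a rate ratio of 0.8:

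| r | CV 0.4: unadjusted / strata / strata + continuous | CV 0.5: unadjusted / strata / strata + continuous | Unadjusted type I error |
|---|---|---|---|
| 0 | 89.5 / 89.8 / 89.7 | 75.4 / 75.8 / 75.8 | 5.5–5.9% |
| 0.3 | 90.2 / 91.2 / 92.0 | 76.5 / 78.3 / 79.6 | 4.8% |
| 0.5 | 90.8 / 93.5 / 95.1 | 77.2 / 82.1 / 85.3 | 3.6–3.8% |
| 0.7 | 92.3 / 95.9 / 98.7 | 79.4 / 88.1 / 94.3 | 2.3–2.6% |

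Type I error of the adjusted models was 5.3–6.1%.

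**Step 4. Cross-checks.**

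- Facility-level log-rate regression on the same data, CV 0.5, same order of models: 75.1/76.8/77.8 (r = 0.3), 76.0/80.5/84.0 (r = 0.5), 78.0/87.0/93.4 (r = 0.7).
- A separate simulation set the share of between-facility variance explained by the strata, R², directly. With 120 facilities, CV 0.4 and R² = 0.25, the model standard error without strata is 0.076 against a true spread of 0.067; type I error is 2.9% without strata and 5.1% with them; power is 85% and 90%. A negative binomial fit gives the same contrast (3.2% and 5.5%; 87% and 92%).
- If transfer rates differ between corporations as readmission does (13/17 = 0.76, an assumption), the gains from strata in the Step 3 model at r = 0/0.3/0.5/0.7 are 1.5/2.1/3.6/4.3 points (CV 0.4) and 1.6/3.5/5.9/9.8 points (CV 0.5).

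**The case against.** The strongest reply is that Section 9.2 does promise covariates, so a model with none would contradict the plan, and the unnamed set may well include the strata. That is fair. It means the defect is missing pre-specification, not a decision to leave the strata out, and the power figures describe what happens only if 9.5 is followed as written.

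The other limits also stand:

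- **Size.** r is assumed. The baseline year is 2017, and Section 13 records a significant effect of COVID-19 on nursing homes, so a low r is possible. At r = 0.3 the strata gain only 1–2 points, and the largest gains need both r = 0.7 and a CV at the plan's upper bound. At CV 0.4, unadjusted power with 142 facilities is already about 90%.
- **Direction.** The error is on the safe side: neither bias nor extra false positives. In the count model the test is clearly conservative only from about r = 0.5, and another fit of that model may be less so. The adjusted count model runs slightly above 5%, so those comparisons are not exactly size-matched; the log-rate and closed-form checks, which show similar gains, limit this worry.
- **Corporations.** Self-reported readmission is not the trial outcome, so the 13% and 17% are only suggestive.

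None of this removes the point. A reader still cannot tell from the plan which covariates enter the primary test, and securing the strata costs almost nothing even if they turn out to predict nothing.

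**Conclusion.** The concern holds. The plan stratifies on two factors, promises covariates, names none, and describes a primary model that contains neither factor. Fitted that way, it forgoes nothing if the strata do not predict transfers, and roughly 3–5 points of power at r = 0.5 or 4–9 at r = 0.7 if they do; the continuous baseline is worth up to about 6 points beyond that. These figures assume 142 facilities, about 50 resident-years each, a rate ratio of 0.8, a CV of 0.4 to 0.5 and a two-sided 5% test. They measure achievable power, and the stated 81% is not put in doubt by this point. The matter should be corrected but does not threaten the trial's validity. Confidence in the textual gap is high; confidence in its size is moderate, because r is unknown.

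**What to change.** In Section 9.5, list the covariates that 9.2 refers to and state that the primary model includes fixed effects for corporation and for the low/high baseline stratum. As a further efficiency gain, add the facility's log 2017 transfer rate as a continuous covariate. Use the same terms in the models for hospice enrollment and death in hospital when those are written out. Settle this before outcomes are compared by arm, and do not let the balance tests decide which terms enter.

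The cost is one sentence. As main effects the two factors use two degrees of freedom, and three with the continuous baseline, against 142 facilities. Because the low/high cut is specific to each corporation, the four cells could be fitted instead for one more. No new data are needed, since the 2017 rates were required to stratify the facilities. At r = 0 the simulated power is unchanged (89.5% against 89.8% at CV 0.4; 75.4% against 75.8% at CV 0.5).
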